## **Protocol**

As humans age, there is a gradual loss of skeletal muscle mass and strength, termed sarcopenia (1,2). The underlying causes of sarcopenia are yet not fully elucidated but are thought to be multifactorial and include increased levels of systemic pro-inflammatory cytokines, a decrease in anabolic hormones and changes in the neuromuscular system (3,4). Furthermore, physical inactivity, chronic diseases, immobilisation and hospitalisation are known to play an important part in the development of sarcopenia (4). Notably, muscle strength declines more rapidly than muscle mass with aging (3) and muscle weakness in the elderly is prevalent and closely linked to frailty, functional decline, immobility, falls, and injuries in this population (5). As such, measures of muscle strength and functional performance have shown to be sensitive markers of frailty in combination with appendicular muscle mass (5,6).

The prevalence of sarcopenia ranges from 20-30% (aged >70yrs) within the general community (2,7). However, the prevalence of sarcopenia in geriatric patients after an acute hospital admission is substantially higher, estimated at  $\approx$ 50% (8). Furthermore, successive events of hospitalisation have been suggested to contribute to the development of sarcopenia, as even short periods (4-5 days) of skeletal muscle disuse are known to induce muscle atrophy (9,10). Mean length of hospital stay in geriatric wards due to acute illness or hip-fracture is typically 7 to 11 days during which the level of physical activity is strongly reduced (11, 12) leading to an accelerated loss of muscle mass that many older patients never recover from.

Notably, a substantial part of the deterioration in functional capacity could be avoided *just* by counteracting loss of muscle mass during hospitalization. As such, we need to identify sensitive biological, clinical and functional biomarkers for loss of muscle mass and function during hospitalization to identify patients at risk of developing sarcopenia and investigate the association of these biomarkers with hospital length of stay, readmissions, mortality, and discharge to a higher level of care.

## **Purpose of the study**

The overall aim of the present study is to identify clinical, functional and biological biomarkers associated with length of hospital stay in older acutely ill patients. In addition,

we will examine sensitive biomarker assays to investigate whether biomarkers assays in combination with clinical and functional measures have the ability to predict loss of muscle mass and function in patients hospitalized in a geriatric ward. Collectively, these initiatives will have the potential to identify patients at risk of developing sarcopenia and thus develop individualized treatments that counteract physical deconditioning and improve independent life expectancy and quality of life in older people, and lead to substantial health-care savings.

**The specific aims of the present project are therefore to:**

- I. Examine whether the level of a variety of biomarkers at admission are associated with length of hospital stay, time to first readmission within 90 days, and time to mortality within 90 days in old patients, and whether the combination of clinical and functional measures with these biomarkers can identify patients at risk of prolonged hospital stay, readmissions and mortality. Primary end-point is length of stay. Secondary end-points are time to first readmission, time to mortality, muscle mass, muscle strength and frailty score (WP1).
- II. Establish biomarker assays for predicting muscle loss and loss of function in old patients hospitalized at a geriatric ward, assessing whether levels of a variety of biomarkers combined with clinical and functional measures are associated with length of hospital stay, readmissions, mortality and whether patients are discharged to a higher level of care. Primary end-points are the relative change in muscle mass, muscle strength and muscle function. Secondary end-points are length of stay, time to first readmission, time to mortality, frailty score and discharge to a higher level of care (WP2)

**Background of the project**

**Physiological adaptations to ageing**

It is well established that human skeletal muscle function decays with aging, and sarcopenia is now generally used to describe the age-related loss of muscle mass and strength, which is believed to play a major role in the pathogenesis of frailty and functional impairment that may occur with old age (13-19). The exact mechanism behind the loss of muscle strength observed with aging and development of sarcopenia is not yet elucidated

(20). However, increased levels of systemic pro-inflammatory mediators such as TNF- $\alpha$ , IL-6 and CRP, a decline in anabolic hormones and changes in the neuromuscular system have been identified as some of the contributing factors (3,4, 21, 22, 23). Furthermore, physical inactivity, chronic diseases, immobilization and hospitalization are known to play a part in the development of sarcopenia (4). In addition, it has been demonstrated that the age-related muscle atrophy is followed by an increased infiltration of non-contractile components within the muscle tissue, such as connective tissue and intramuscular fat (24;25). Considering these morphological changes it is not surprising that maximal muscle strength is reduced as a result of aging by approximately 1.5 % per year from the sixth decade and forth (26).

### **Sarcopenia**

Skeletal muscle tissue accounts for almost half of the human body mass and, in addition to its power-generating role; it is a crucial factor in maintaining homeostasis of glucose metabolism and as an energy reservoir in catabolic conditions. Given its central part in human mobility and metabolic function, any deterioration in the contractile, material, and metabolic properties of skeletal muscle has an extremely important effect on human health.

Sarcopenia specifically refers to the skeletal muscle atrophy and loss of muscle strength and function often observed with aging and is a major musculoskeletal cause of the loss of mobility, independence, and frailty in older adults. It typically appears as a decrease in muscle strength concurrent with a decrease in muscle mass. Clinical sarcopenia has been defined in statistical terms assuming a lower normal limit of two standard deviations below a mean relative appendicular muscle mass referred to findings in young healthy adults (27). The prevalence of sarcopenia ranges from 20-30% (age > 70years) within the general community (2,7), however, the prevalence of sarcopenia in geriatric patients after an acute hospital admission is substantially higher estimated at  $\approx$ 50% (8). The etiology of sarcopenia is complex and involves neuronal, hormonal, immunological and nutritional mechanisms. Furthermore, physical inactivity and immobilization is known to play an important part in the development of sarcopenia (28;29). Yet, muscle mass in old age is not only lost due to reduced anabolism and increased catabolism, but also due to a reduced capacity of muscle

regeneration as muscle stem cell activation and proliferation becomes impaired in old age (30).

The knowledge surrounding the prevalence and determinants of sarcopenia in geriatric rehabilitation care is scarce, and it is unknown whether specific biomarkers can predict physical deconditioning during hospitalization. As such, the development of novel interventions for this group of patients is hampered by the lack of understanding of the basic biological mechanisms driving sarcopenia in conjunction with other age-related diseases in humans. The importance of sarcopenia has recently been underlined by its inclusion as a reportable disease in the Centers for Diseases Control and Prevention (ICD-10-CM code M62.84) in October 2016 (31). However, despite the serious consequences of sarcopenia being widely recognized, the diagnose has yet to be implemented in clinical practice in Denmark. Lack of knowledge and systematic assessment hinders diagnosis and treatment of sarcopenia and leads to physical deconditioning during hospitalization. Consequently, more than 50% of geriatric patients report a decline in functional capacity after discharge, often leading to a need for prolonged and expensive rehabilitation interventions (8).

As successive events of hospitalisation have been suggested to contribute to the development of sarcopenia, and even short periods (4-5 days) of skeletal muscle disuse are known to induce muscle atrophy (9,10), we have defined a prolonged hospital length of stay as an admission lasting >96 hours. In addition, we have defined patients discharged to a higher level of care as patients receiving increased relief, patients with increased need for a caregiver, patients referred to rehabilitation or 24-hour care, or patients moving to a nursing home following discharge. Readmission data will be limited to readmissions in the region of Zealand and the Capital Region of Denmark.

## **Biomarkers**

Mechanisms that regulate skeletal muscle mass are central to the understanding of sarcopenia and related geriatric syndromes. Recently, GDF11, a close family member to myostatin (33), has been measured in human blood samples (34). When GDF11 is added to muscle and animals, identical signaling patterns to myostatin are seen with consequent myotube and muscle atrophy and inhibition of muscle differentiation (32,35). High circulating GDF11 levels have been related to increased disease burden and elevated risk of post-operative complications and mortality in older adults undergoing heart surgery. Notably,

patients categorized as frail based on low grip strength and gait speed as well as self-reported activity measures, had significantly higher GDF11 levels compared to non-frail controls (34). The data indicate that measurements of circulating GDF11 could be a biomarker that reflect frailty and related to geriatric syndromes. However, translation of these new findings into clinical utility needs further validation in a larger cohort.

In addition to the atrophic effects of GDF11, it is also able to induce expression of GDF15 (36). GDF15 is present in low levels under healthy conditions but can increase during disease or injury and contribute to muscle wasting by suppressing appetite, resulting in anorexia and drastic weight loss (37). In elderly, unintentional weight loss has been associated with increased in hospital morbidity and increased overall mortality (38). In an animal study, the suppression of appetite but not the loss of skeletal muscle could be reversed with a GDF15-neutralizing antibody (36). As such, the combined effects of GDF11 and GDF15 in muscle wasting during hospitalization might affect the length of hospital stay, readmissions and mortality.

A decrease in hormone concentrations appears to be associated with the development of sarcopenia. Especially in men, the decline in testosterone levels seems to be associated with a decline in muscle mass and muscle strength (39). Indeed, testosterone can increase protein synthesis in muscle and promote muscle regeneration by activating satellite cells (40). Estrogen may also promote muscle repair by activation and proliferation of satellite cells via the estrogen receptor  $\alpha$  and  $\beta$  (41, 42). In addition, a murine study showed that ovariectomized rats (OVX) was unable to fully regain their muscle mass following a period of hindlimb unloading with a subsequent period of reloading compared to OVX rats with estrogen supplementation (43). The protective effect of estrogen on muscle mass during hindlimb unloading and reloading was also confirmed in a study of male rats (44) As such, estrogen might attenuate the degree of disuse atrophy.

Studies have demonstrated that ageing is accompanied by modifications of the immune system, specifically immunosenescence, leading to cytokine dysregulation and a chronic low-grade inflammation (45, 46). This has potential detrimental consequences, as research has shown that biomarkers of inflammation are associated with the pathology of the most common chronic age-related diseases including atherosclerosis (47), chronic heart failure (48), osteoporosis (49), type II diabetes mellitus (50), neurodegenerative disorders (51,52)

and sarcopenia (53, 54, 55). Several studies have investigated the association of inflammatory biomarkers with muscle mass, muscle strength and muscle function. In vitro, exposure of myoblasts to TNF- $\alpha$  inhibits muscle differentiation and causes a decrease in protein synthesis (56). In addition, TNF- $\alpha$  binding to its receptor TNFR activates the NF- $\kappa$ B pathway causing proteolysis (57). However, results regarding the effect of inflammatory biomarkers on muscle mass are inconsistent and lack clear evidence as to whether these inflammatory biomarkers are associated with sarcopenia.

Many studies have assessed low-grade inflammation by measuring a limited number of inflammatory proteins, and one study showed that elderly individuals exhibiting high levels of pro-inflammatory cytokines also tended to show high levels of anti-inflammatory cytokines (58). Thus, we aim to include a variety of both pro- and anti-inflammatory markers.

Furthermore, distinct patient populations with co-existing pathophysiological processes might exhibit different biomarker profiles. A recent study found a negative association between systemic levels of CRP and changes in muscle mass in geriatric patients in response to resistance training during hospitalization, indicating that patients with inflammation during their hospital stay may have an increased risk of deconditioning during hospitalization (59).

Regardless, systemic levels of the inflammatory marker C-reactive protein (CRP), has been found to be predictive of both the length of hospital stay and readmissions (60, 61). Indeed, geriatric patients with inflammation at admission stayed on average 3 days longer than patients without inflammation, evaluated by CRP levels at admission (62). Despite CRP being a nonspecific marker of inflammation, it has also been recognized as a predictive marker of in-hospital mortality in elderly patients admitted to the acute ward (63).

Recently, suPAR was established as a biomarker of inflammation and immune activation, and elevated levels of suPAR are believed to reflect a state of chronic inflammation (64). suPAR correlates with other inflammatory markers, such as TNF- $\alpha$ , and patients with the highest levels of suPAR generally have the worst prognosis (65). Elevated levels of suPAR have been associated with increased risk of cardiovascular disease, cancer, type II diabetes and premature mortality in the general population, independent of CRP levels (66). However, a recent study found that the prognostic capability of suPAR did not affect all-cause mortality in patients admitted to the emergency department (67).

In a study of HIV-infected patients, suPAR was associated with low muscle mass, while IL-6 was associated with both low muscle mass and increased fat mass in both patients and healthy controls (68). Thus, there seem to be distinct inflammatory processes occurring simultaneously with different effects on muscle mass and fat mass, respectively.

Further validation needs to be conducted in different patient populations to utilize the possible prognostic value of these biomarkers, either individually or in combination with functional and clinical measures.

## **RESEARCH PLAN**

This project includes 2 work packages (WP), of which WP1 is a prospective cohort study of acutely ill older patients (65+ years) referred to the hospital and will investigate the association of biomarkers combined with clinical and functional measures with length of hospital stay, time to first non-elective readmission, muscle mass, muscle strength, frailty, and time to mortality. WP2 is a prospective cohort study of older patients (>65 years) admitted to a geriatric ward for treatment of the acute disease and rehabilitation care and will investigate the possible association of biomarkers with the relative change in muscle mass and function, frailty score, length of hospital stay, time to first non-elective readmission, time to mortality and discharge to a higher level of care. Readmission data will be limited to readmissions in the region of Zealand and the Capital Region of Denmark.

### **WP1: Biomarkers in the acutely ill older patient**

**Hypothesis:** We hypothesize that combining clinical and functional measures with systemic biomarkers has the potential to identify older acutely ill medical patients at risk of prolonged (>96 hours) hospital stays, non-elective readmissions, and mortality.

**Overview of Actions:** Acutely ill medical patients (age >65 years) referred to Bispebjerg-Frederiksberg Hospital will consecutively be enrolled in the study. We will recruit participants during a 1-year period.

**Assessments:** Blood tests, frailty (CSHA Clinical Frailty Scale), risk of pressure ulcers (Braden Score), sarcopenia (SARC-F), hand-grip strength, chair-rise test and body composition (BIA). Blood samples will be used to assess biomarkers of muscle atrophy and wasting (GDF-11 & GDF-15), inflammatory cytokines and acute-phase proteins, sex hormones and immune activation (suPAR). All assessments will be performed within the

first 24 hours of admission. Primary endpoint is length of hospital stay. Secondary endpoints are time to first non-elective readmission, time to mortality, muscle strength, muscle mass and frailty.

### **WP2: Biomarkers for changes in muscle mass and function in geriatric patients**

**Hypothesis:** We hypothesize that combining clinical and functional measures with biomarkers will give us the opportunity to elucidate a composition of biomarkers associated with the change in muscle mass and function during hospitalization, thus having the potential to identify future geriatric patients at risk of physical deconditioning and prolonged (>96 hours) hospital stays, non-elective readmissions, mortality, and discharge to a higher level of care.

**Overview of Actions:** Geriatric patients (age >65 years) referred to geriatric rehabilitation care at Bispebjerg-Frederiksberg Hospitals will be enrolled in the study. We will recruit participants during a 1-year period.

**Assessments:** Included patients will be monitored by blood tests immediately following admission and at discharge. A geriatric assessment will be performed during admission (Barthel Index, the CSHA Clinical Frailty Scale, SARC-F, the Orientation-Memory-Concentration test (OMC) and De Morton Mobility Index (DEMMI). Measurements of muscle function (e.g. hand-grip strength, gait-speed and sit-to-stand tests) and body composition (BIA) will be performed shortly after admission and at discharge. Blood samples will be used to assess biomarkers of muscle atrophy and wasting (GDF-11 & GDF-15), inflammatory cytokines and acute-phase proteins, sex hormones and immune activation (suPAR). Preliminary assessments will be performed within the first 24 hours of admission. Primary end-points are relative change in muscle mass, muscle strength and muscle function. Secondary end-points are length of hospital stay, time to first non-elective readmission, time to mortality, frailty, and discharge to a higher level of care.

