### **Project significance and future perspectives**

The project includes; 1) Identifying biomarkers in acutely ill older patient groups associated with length of hospital stay, non-elective readmissions, muscle mass, muscle strength, frailty, and time to mortality within 90 days. 2) Combining biomarker measurements with clinical and functional measurements for predicting loss of muscle mass and function

during hospitalization in geriatric patients, and investigating the association with hospital length of stay, non-elective readmissions, time to mortality, frailty, and discharge to a higher level of care. The findings of the study will not only have implications for geriatric patients but has the potential to be translated across disciplines to any patient at risk of hospital induced muscle wasting.

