## **Subjects and methods**

### **Subjects**

Acutely ill medical patients (age > 65 yrs) for WP1 (n=1100) will be enrolled ad hoc from Bispebjerg-Frederiksberg Hospital.

Geriatric patients (age > 65 yrs) for WP2 (n=200) will be enrolled ad hoc from Bispebjerg-Frederiksberg Hospital.

For both WP1 and WP2 we aim to include patients with a dementia diagnosis and patients with delirium, as this group of patients represent a large portion of the elderly patients admitted to the hospital. Thus, the project aims to be representative of the general elderly patient population. Patients with dementia will be identified through patient journals. Depending on the severity of dementia and delirium, it might be possible that some patients are unable to sign participant consent, and in these cases, we will seek participant consent from a close relative or guardian. Independent medical doctors who have knowledge of the project but are not associated with the project and are independent to the interests of the principal investigator will evaluate whether these subjects are able to participate in the study. The medical doctors designated to perform this evaluation is chosen based on available independent doctors on duty in the department that day. Two large prospective cohort studies have previously reported that dementia is independently associated with frailty (69,70). Another study has shown that frail patients have an increased risk of developing delirium and that frail patients with delirium have a reduced survival rate following hospitalization compared to non-frail patients with delirium (71). This puts this specific patient population at increased risk of adverse outcomes and muscle wasting during hospitalization. As such, it is essential that we increase our knowledge of the underlying mechanisms and predictors of muscle wasting and the predictors of longer hospital stays and mortality in this specific patient population so that we might help future

patients with dementia and delirium. The project entails minimal discomfort for the subjects and has no permanent side effects. Should the patients with delirium regain their legal competency during their hospital stay, they will have to sign an independent participant consent.

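### WP2's primary function endpoint, relative change, is undefined at an admission score of 0 and unstable near 0; sit-to-stand and gait speed should be analysed on the measured scale

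*Combined protocol and SAP*

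**What the plan says.** The WP2 section of the Research plan sets the endpoint: "Primary end-points are relative change in muscle mass, muscle strength and muscle function". The specific aims agree: "Primary end-points are the relative change in muscle mass, muscle strength and muscle function". The Research plan overview frames WP2 as a study to "investigate the possible association of biomarkers with the relative change in muscle mass and function".

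The function tests form an open list: "Measurements of muscle function (e.g. hand-grip strength, gait-speed and sit-to-stand tests". Timing is also given: "gait-speed and sit-to-stand tests) and body composition (BIA) will be performed shortly after admission and at discharge". The Methods section adds that sit-to-stand runs for 30 seconds and that gait speed is taken at habitual and maximal pace.

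Overall outcome analysis plans a multivariate linear regression for loss of muscle mass and function. Its only rule for incomplete data is a single sentence saying that missing values are imputed.

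The Exclusion criteria do not mention inability to rise or walk, and under Subjects the sponsor writes: "we aim to include patients with a dementia diagnosis and patients with delirium". Statistical considerations lists inability to do the tests among the reasons for an expected 20% participation.

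The documents give no formula for relative change, no rule for an admission score of 0, and no way to record a patient who cannot perform a test.

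**The concern.** Relative change divides by the admission score. That is harmless for BIA muscle mass, which is never near 0, and rarely a problem for grip. A count of stands in 30 seconds, or a walking speed, can be 0 or close to it in acutely ill geriatric patients. A patient at 0 then has no endpoint, although the 0 is a valid observation. A patient at 1 or 2 can produce changes of 100% or more from a difference of one or two stands. Least squares gives such values great weight, so a handful of the weakest patients can decide which biomarkers appear associated with loss of function.

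The second exposure is at discharge. If a patient who can no longer do the test were recorded as missing, the imputation rule would replace a known loss of ability with a score typical of patients who kept it. That would erase the deconditioning that WP2 wants to predict.

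**Working it through.** The plan gives no SD, effect size or power for the WP2 change endpoints, so there is no stated figure to reproduce. From the documents come n=200, the endpoint scale, the tests and the linear model. Every distribution below is an assumption.

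**1. Algebra.** With A the admission score and D the discharge score, take relative change as 100 × (D − A)/A, the usual form. At A = 0 it is undefined. For D − A = 1:

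- A = 1: +100%
- A = 2: +50%
- A = 8: +12.5%
- A = 12: +8.3%

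Each 5% of patients at A = 0 removes 0.05 × 200 = 10 patients from the endpoint.

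**2. Weight of the low scorers.** Simulated sit-to-stand counts, n=200, mean 6 to 8, SD 3 to 5, error SD 1, true-change SD 1 or 2, admission zeros removed. Patients scoring 1 or 2 are 3 to 12% of the sample. They carry about 39 to 68% of the variance of relative change (34 to 65% in repeat runs) and 3 to 10% of the variance of absolute change.

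**3. Power for a biomarker.** A second model: counts floored at 0, error SD 1.5 per visit, n=200, 2,000 replicates. The zero counts and variance shares are from runs with no true change. Power is for a biomarker effect of 0.6 stands per SD and a true-change SD of 1.5.

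| Latent mean/SD | Score 0 at admission | Score 1–2 (of those above 0) | Their share of relative-change variance | Power: relative, zeros dropped | Power: absolute change, all | Power: discharge adjusted for admission, all |
|---|---|---|---|---|---|---|
| 4/4 | 20% | 20% | 71% | 0.57 | 0.83 | 0.86 |
| 6/4 | 10% | 12% | 64% | 0.63 | 0.87 | 0.90 |
| 8/4 | 4% | 6% | 53% | 0.65 | 0.89 | 0.90 |
| 10/3 | 0.2% | 1% | 24% | 0.76 | 0.90 | 0.92 |

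A separate rerun gave 0.62 to 0.77 for relative change and 0.86 to 0.93 for the two measured-scale analyses. In the last row almost nobody scores 0, yet the gap remains, so the loss of power is not only a matter of dropped patients.

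**4. The two measured-scale models agree.** If D = a + b × marker + c × A, then D − A = a + b × marker + (c − 1) × A. In a numerical check the marker coefficient was 0.418 either way, and c moved from 0.943 to −0.057.

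**5. Imputation, only if inability is recorded as missing.** Suppose a mean of 8 stands and 5 to 15% losing the ability, unrelated to admission score. Scoring them 0 shifts the mean change by −0.05 × 8 = −0.4 to −0.15 × 8 = −1.2 stands; imputing them from able patients with no average change gives about 0. The shift is smaller if mainly weak patients lose the ability.

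**6. A test's own admission score as predictor.** With no true change and equal variances, corr(A, D − A) = −√((1 − reliability)/2), which is −0.32, −0.22 and −0.16 at reliability 0.80, 0.90 and 0.95. For a grip-like measure the relative-change values are −0.34, −0.24 and −0.17. The two scales are nearly alike.

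**The case against.** **Few patients may be affected.** Statistical considerations expects inability to reduce participation, and the list of function tests is open and includes grip. If grip alone carried the function endpoint, little of this point would remain. That stands as a limit on size. It does not settle the matter: an expectation about recruitment is not an analysis rule, it cannot cover a patient who loses the ability by discharge, and gait speed and sit-to-stand are both named.

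**The power comparison favours the measured scale.** The simulated biomarker adds a fixed number of stands. A marker acting in proportion to the admission score would do relatively better on the relative scale. That is fair, but it does not make the ratio defined at 0 or stable at 1 or 2.

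**Stronger readings that the documents do not support:**

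- A reader might infer that the plan will impute away known inability. No section says inability is recorded as missing, so this harm is conditional.
- Since the aims speak of "Combining biomarker measurements with clinical and functional measurements for predicting loss of muscle mass and function", a reader might infer that a test's own admission score will be entered against its own change, and that the results will be artefact. The plan does not state that model; the functional measures could be other tests. The coupling is almost equal for absolute change, so it is not a fault of the relative endpoint, and a biomarker unrelated to the admission score is not affected.
- A reader might put the weight of low scorers as high as 24% of patients carrying 80% of the variance. That arises only if would-be zeros are set to 1, which counts again the patients already treated as undefined.

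**Conclusion.** The point holds for sit-to-stand and gait speed. As written, the primary function endpoint has no value for a patient at 0 on admission, and a small group of low scorers dominates it. That part is algebra. Its size rests on assumed distributions: about 39 to 68% of the variance carried by 3 to 12% of patients, and power of 0.57 to 0.77 against 0.83 to 0.93 at n=200 for an additive effect of 0.6 stands per SD. All of the simulated figures are for sit-to-stand counts; gait speed shares the algebra but was not simulated. The number of patients at or near 0 cannot be derived from the documents. Muscle mass is unaffected and grip rarely so. The change should be made, with medium confidence about how much it matters.

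**What to change.** For sit-to-stand and gait speed, make the primary analysis the discharge score with the admission score as covariate (equivalently, absolute change adjusted for admission score), and keep relative change as descriptive. State which test or tests carry muscle function. Score physical inability as 0 at either visit; code refusal or cognitive inability separately, and impute only those. Relative change may stay for muscle mass and grip, with its formula stated.

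As a note only: if a test's own admission score is in the model, do not read its coefficient or AUROC as prediction of deconditioning, because measurement error alone produces a negative association on the absolute or the relative scale.

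The cost is SAP wording plus one reason code for a test not done, which must be in place during data collection; admission values are already planned. The downsides are:

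- Function effects are no longer in per cent.
- Zero-heavy scores may need a robust or ordinal model.
- A patient at 0 on admission cannot show further loss.
- With measurement error, the adjusted analysis can be biased for a marker correlated with true admission function, so show unadjusted absolute change as a sensitivity analysis.

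Do not go further and require the adjusted and unadjusted results to agree in sign and significance. On assumed inputs that rule can cut power from 60% to 22%, and it still passes 32 to 84% of markers that only track a transient admission state.
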